19. PHARMACOKINETICS

Plasma concentrations of etrasimod, and if warranted M3 (AR503641) and M6 (AR504344), will be assessed from samples collected prior to dosing and 4 hours (\pm 15 minutes) post-dose (after ECG) on Week 0/Day 1, samples collected prior to dosing (trough) at Weeks 4, 8, 16, 24 of the double-blind period, and Weeks 28, 32, 46, 52 or the ET visit, if applicable, of the extension period. Additionally, a 4-Week Safety Follow-up visit sample is being collected. Concentrations below the limit of quantification (BLQ) will be assigned a numerical value of zero for the calculation of descriptive statistics in concentrations (except for geometric mean and geometric %CV) and plotting of concentrations. For geometric mean and geometric %CV, the zero values will be excluded.

The pharmacokineticist will determine the strategy for dealing with data affected by protocol deviations or events which may impact the quality of PK concentration data on a case-by-case basis with input from the Pfizer study physician and Pfizer clinical pharmacologist, as needed. Examples for protocol deviations or events include, but may not be limited to, vomiting on the day prior to trough sample collection, sample processing errors that lead to inaccurate bioanalytical results, and/or inaccurate dosing prior to PK sampling. In the case of an important protocol deviation or event, the affected PK data collected may be excluded from the summaries, calculation of the average steady state trough plasma concentration (C_{trough}) based on Week 4 to Week 24 trough concentrations ($C_{\text{trough,ss,W4-W24}}$), exposure-response analysis, and/or population PK analysis, but will still be reported in the study result listings.

Unless otherwise specified, PK summaries will use the Pharmacokinetic Set. Exposure-response analysis will use the Safety Set.

Individual subject etrasimod plasma concentrations (and etrasimod metabolites, if applicable) will be presented in the data listings, including subject ID, treatment received, sex, age, weight, nominal timepoint, actual blood collection date/time, concentration, and time since last dose, and also summarized using descriptive statistics (n, mean, SD, %CV, geometric mean, geometric % CV, median, minimum, and maximum) by nominal timepoint and treatment.

All subjects are expected to achieve steady-state plasma concentration by Week 2. For each subject, the average steady state trough (pre-dose) plasma concentration (C_{trough}) based on Week 4 to Week 24 trough concentrations ($C_{\text{trough,ss,W4-W24}}$) per subject will also be calculated and presented in a data listing and summarized using descriptive statistics by treatment.

Mean (\pm SD) etrasimod concentration versus nominal time will be plotted by treatment on linear scale for the double-blind period and the extension period separately. Additionally, a mean (\pm SD) concentration-time plot with etrasimod and metabolites overlaid on linear scale will be generated for each treatment for the induction period and the extension period separately.

Box plots of etrasimod, M3, and M6 concentrations at Day 1, 4 hour post-dose timepoint ($C_{4\text{hr}}$) and steady-state C_{trough} (Weeks 2 through 24 [$C_{\text{trough,ss,W4-W24}}$]) will be plotted versus nominal timepoint on ordinal scale, separately by treatment. Similarly, box plots of etrasimod, M3, and M6 concentrations will be presented for the extension phase by treatment.

Individual subject plasma concentrations versus actual time will be plotted since start of treatment on linear scale for the induction period (Weeks 0 to 24) and the extension period (Weeks 28 to 52) separately. Individual subject plots with etrasimod and metabolite concentration data will be overlaid on the same plot.

Scatter plots of individual subject average steady-state $C_{\text{trough ss,W4-W24}}$ versus Baseline body weight and versus Baseline age as continuous variables will be generated by treatment for the Pharmacokinetic Set, which will also include the Spearman's rank correlation coefficient, p-value, and LOESS trend line.

To explore potential etrasimod plasma exposure-response relationships, the following scatter plots will be generated in the Safety Set, including data from placebo subjects (plotted at 'zero' concentration). Any contributing data from the placebo subjects will be annotated with a different color or symbol. All scatter plots will include the Spearman's rank correlation coefficient, p-value, and LOESS trend line (based on subjects that received active treatment only).

- Individual subject percentage change in esophageal PEC versus etrasimod steady-state C_{trough} at Week 16
- Individual subject lymphocytes versus etrasimod steady-state C_{trough} by visit (Weeks 4 through 24)
- Individual subject absolute changes from Baseline in lymphocytes versus etrasimod steady-state C_{trough} by visit (Weeks 4 through 24)
- Individual subject percent changes from Baseline in lymphocytes versus etrasimod steady-state C_{trough} by visit (Weeks 4 through 24)
- Individual subject heart rate versus etrasimod concentration at matching visit/timepoint (Day 1 through Week 24): two-panel plot with Day 1 on the left and Weeks 4 through 24 on the right
- Individual subject absolute changes from Day 1 Pre-dose in heart rate versus etrasimod concentration at matching visit/timepoint (Day 1 through Week 24): two-panel plot with Day 1 on the left and Weeks 4 through 24 on the right

Furthermore, the following overlay plots will be generated in the Pharmacokinetic Set within the etrasimod group only:

- Mean (SD) absolute change from Baseline in lymphocytes and mean (SD) etrasimod concentration versus nominal timepoint (Weeks 0-24)
- Mean (SD) percent change from Baseline in lymphocytes and mean (SD) etrasimod concentration versus nominal timepoint (Weeks 0-24)
- Mean (SD) heart rate and mean (SD) etrasimod concentration versus nominal timepoint (Weeks 0-24)
- Mean (SD) absolute change from Baseline in heart rate and mean (SD) etrasimod concentration versus nominal timepoint (Weeks 0-24)

All summary figures, with the exception of the etrasimod and metabolite overlay plots, scatter plots of individual subject $C_{\text{trough,ss,W4-W24}}$ values versus Baseline body weight and versus Baseline age, scatter plots of individual subject heart rate versus etrasimod concentration at matching visit/timepoint (Day 1 through Week 24), and scatter plots of individual subject absolute changes from Day 1 Pre-dose in heart rate versus etrasimod concentration at matching visit/timepoint will be repeated by:

- Sex
- Weight (\leq Median or $>$ Median)
- Age at consent
- Tobacco use (Yes/No)

The plasma concentrations over time will be used in a population PK analysis, which will be described in a separate plan.

20. DATA NOT SUMMARIZED OR PRESENTED

The other variables and/or domains not summarized or presented are:

- Comments

These domains and/or variables will not be summarized or presented, but will be available in the clinical study database, SDTM and/or ADaM datasets.

APPENDIX 1. PROGRAMMING CONVENTIONS FOR OUTPUTS

Output Conventions

Outputs will be presented as shown in the Output shells.

Decimals, Percentages, and P-Values

- If the original data has N decimal places, then the summary statistics should have the following decimal places:
 - Minimum and maximum: N
 - Mean (and LS Means), median (and Q1, Q3): N + 1
 - SD or SE: N + 2
 - Percentages will be reported to one decimal place. Where counts are zero, percentages will not appear in the output.
 - P-values will be reported to four decimal places, except values <1.000 but >0.999 will be presented as '>0.999' (e.g., 0.9998 is presented as >0.999); and
 - values <0.0001 will be presented as '<0.0001' (e.g., 0.00009 is presented as <0.0001). Rounding will be applied after the <0.0001 and >0.999 rule.

Dates & Times

Depending on data available, dates and times will take the form DDMMYYYY or DDMMYYYY:hh:mm.

Spelling Format

English US.

Presentation of Treatment Groups

For outputs, treatment groups will be represented as follows and in that order:

Treatment Group	For Tables and/or Graphs	For Listings
etrasimod 2 mg	etrasimod 2 mg	etrasimod 2 mg
etrasimod 1mg	etrasimod 1 mg	etrasimod 1 mg
etrasimod any dose*	etrasimod any dose	Placebo
Placebo	Placebo	Screen Failure
Screen Failure	Screen Failure	

Treatment Group	For Tables and/or Graphs	For Listings
Not Treated**	Not Treated	Placebo

* To be used for tables and/or graphs only.

** To be used for subjects in safety listings who are randomized but do not receive study drug.

Presentation of Visits

For outputs, visits will be represented as follows and in that order when applicable:

Visit Name*	Study Period
Screening	Screening
Baseline, Day 1, Week 2, Week 4, Week 8, Week 16, Week 20, Week 24	Double-Blind Treatment
Week 28, Week 32, Week 46, Week 52	Extension Treatment
2-Week Follow-Up, 4-Week Follow-Up	Safety Follow-Up

- *If a visit is not available for a certain analysis, it won't be displayed

LISTINGS

All listings will be ordered by the following (unless otherwise indicated in the template):

- Randomized treatment group (or treatment received if it's a safety output), first by Etrasimod 2 mg, Etrasimod 1 mg, then Placebo, then Screen Failure and then No Treatment (only in safety listings if there are any randomized subjects who did not receive study drug)
- Subject number (which is expected to incorporate study site/center),
- Date (where applicable)

APPENDIX 2. PARTIAL DATE CONVENTIONS

Imputed dates will NOT be presented in the listings.

ALGORITHM FOR TREATMENT EMERGENCE OF ADVERSE EVENTS:

AE START DATE	AE STOP DATE	ACTION
Known	Known, Partial or Missing	If AE start date < study drug first dose date, then not TEAE If AE start date \geq study drug first dose date, then TEAE
Partial, but known components show that it cannot be on or after date of first dose of study drug	Known, Partial or Missing	Not TEAE
Partial, could be on or after date of first dose of study drug	Known	If AE stop date < study drug first dose date, then not TEAE If AE stop date \geq study drug first dose date, then TEAE
	Partial	Impute AE stop date as latest possible date (i.e. last day of month if day unknown or 31st December if day and month are unknown), then: If AE stop date < study drug first dose date, then not TEAE If AE stop date \geq study drug first dose date, then TEAE
	Missing	Assumed TEAE
Missing	Known	If AE stop date < study drug first dose date, then not TEAE If AE stop date \geq study drug first dose date, then TEAE
	Partial	Impute AE stop date as latest possible date (i.e. last day of month if day unknown or 31st December if day and month are unknown), then: If AE stop date < study drug first dose date, then not TEAE If AE stop date \geq study drug first dose date, then TEAE

AE START DATE	AE STOP DATE	ACTION
	Missing	Assumed TEAE

ALGORITHM FOR PRIOR AND CONCOMITANT MEDICATIONS:

START DATE	STOP DATE	ACTION
Known	Known	If medication stop date < study med first dose date, assign as prior If medication stop date >= study med first dose date, assign as concomitant
	Partial	Impute stop date as latest possible date (i.e. last day of month if day unknown or 31st December if day and month are unknown), then: If medication stop date < study med first dose date, assign as prior If medication stop date ≥ study med first dose date, assign as concomitant
	Missing	If medication stop date is missing could never be assumed a prior medication, assign as concomitant
Partial	Known	Impute start date as earliest possible date (i.e. first day of month if day unknown or 1st January if day and month are unknown), then: If medication stop date < study med first dose date, assign as prior If medication stop date ≥ study med first dose date, assign as concomitant
	Partial	Impute start date as earliest possible date (i.e. first day of month if day unknown or 1st January if day and month are unknown) and impute stop date as latest possible date (i.e. last day of month if day unknown or 31st December if day and month are unknown), then: If medication stop date < study med first dose date, assign as prior If medication stop date ≥ study med first dose date, assign as concomitant
	Missing	Impute start date as earliest possible date (i.e. first day of month if day unknown or 1st January if day and month are unknown), then: If medication stop date is missing could never be assumed a prior medication, assign as concomitant

START DATE	STOP DATE	ACTION
Missing	Known	If medication stop date < study med first dose date, assign as prior Else assign as concomitant
	Partial	Impute stop date as latest possible date (i.e. last day of month if day unknown or 31st December if day and month are unknown), then: If medication stop date < study med first dose date, assign as prior If medication stop date \geq study med first dose date, assign as concomitant
	Missing	Assign as concomitant

APPENDIX 3. QUESTIONNAIRE SCORING INFORMATION

DSQ

The DSQ is a validated patient-reported outcome questionnaire that will be used to characterize baseline dysphagia severity and changes with treatment intervention. Questions 1 and 2 of the DSQ will be used to determine the eligibility regarding active dysphagia during the Screening Period. One episode of dysphagia is counted when a subject responds “yes” to questions 1 and 2. Subjects must have at least an average of 2 episodes of dysphagia per week over 2 weeks during the Screening Period.

The DSQ will be scored over a 14-day period, and a minimum of 8 DSQ daily subject eDiary entries out of the 14-day period preceding the date of scoring are required to calculate DSQ score. The DSQ total score range is 0 to 84.

PGIC

The PGIC is a 1-item questionnaire using a 5-point Likert scale to capture the subject’s overall impression of change in EoE symptoms from Baseline. The recall period is 16 to 52 weeks. The PGIC score range is 1 to 5.

PGIS

The PGIS is a current-state, 1-item questionnaire using a 4-point Likert scale to capture the subject’s overall impression of EoE symptom severity over the past 7 days. The PGIS score range is 1 to 4.

EoE-HSS

The EoE-HSS objectively assesses histologic changes in esophageal mucosa beyond eosinophil number. It describes changes in 8 histologic features and assesses severity (grade) and extent (stage) of abnormalities that are scored using a 4-point scale (0 = normal; 3 = most severe or extensive). The 8 features include:

1. Eosinophilic inflammation
2. Basal zone hyperplasia
3. Eosinophil abscess
4. Eosinophil surface layering
5. Dilated intercellular spaces
6. Surface epithelial alteration
7. Dyskeratotic epithelial cells
8. Lamina propria fibrosis

EREFS

The EREFS will be used to characterize the baseline endoscopic severity of EoE and changes with treatment. Presence and severity of 6 esophageal endoscopic features are scored by the local endoscopist. The endoscopic features include:

1. Fixed Rings
2. Exudates
3. Furrows
4. Edema
5. Stricture
6. Crepe paper esophagus

EoE-QOL-A

The EoE-QOL-A 37-item questionnaire is a disease-specific measure of health-related QOL in adults with EoE. It is scored using a 5-point scale and measures 5 domains:

1. Eating/Dietary Impact
2. Social Impact
3. Emotional Impact
4. Disease Anxiety
5. Choking Anxiety

APPENDIX 4. IDENTIFICATION OF RESCUE THERAPY

This appendix outlines the process the Pfizer clinical team/medical reviewers will use to determine rescue therapy for EoE in the APD334-206 study.

The objective of rescue therapy identification is to establish 1) intercurrent events for the efficacy estimands, and 2) exclusion of subjects from the Per Protocol Set(s).

Per protocol, rescue therapy is defined as any new therapy (ie, medication or procedure) or change in existing EoE therapy used to treat new or worsened EoE symptoms. In addition, use of certain medications/procedures that do not meet the definition of rescue therapy but are deemed to have significant impact on the efficacy assessment will be reviewed and may be considered as rescue therapy.

Only therapies reported on the electronic case report forms (eCRFs) will be assessed for rescue therapy determination. Use of rescue therapy during the follow-up period (beginning on or after the date of last study treatment administration) will not be considered as a rescue therapy.

The list of all rescue therapy uses in the study will be identified and finalized prior to study unblinding.

Medical procedure

- Esophagogastroduodenoscopy (EGD)
 - o Rule:
 - When dilation was done during EGD, any after first dose
 - When dilation was not done during EGD, any EGD with food bolus removal after first dose

Medications

- Proton Pump Inhibitors
 - o Examples of Medications
 - Omeprazole (Prilosec)
 - Lansoprazole (Prevacid)
 - Dexlansoprazole (Dexilant)
 - Esomeprazole (Nexium)
 - Pantoprazole (Protonix)
 - Rabeprazole (Aciphex)
 - o Rules
 - When used for EoE: any new initiation or change in dose after Day 1
 - When used for other disease (eg, GERD): New initiation or change in dose after Day 1 AND
 - Use > 4 weeks at the time of EGD OR
 - Use > 8 weeks with the end of treatment date falling within 4 weeks of EGD
- Corticosteroids
 - o Applicable route of administration: swallowed, oral, IM, SC, IV
 - o Examples of Medications
 - Fluticasone (Flovent)
 - Budesonide (Pulmicort, Flexhaler)
 - Betamethasone
 - Cortisone
 - Deflazacort
 - Dexamethasone
 - Fludrocortisone
 - Hydrocortisone
 - Methylprednisolone
 - Prednisone
 - Prednisolone

- Triamcinolone
- Rules
 - When used for EoE: any new initiation after Day 1
 - When used for other diseases: any new initiation after Day 1 AND
 - Use > 7 days at the time of EGD OR
 - Use > 14 days with the end of treatment date falling within 8 weeks of EGD
- Drugs that have been or are being investigated in clinical trials for the treatment of EoE
 - Examples of medications
 - Anti-interleukin (IL)-5 antibodies (eg, mepolizumab, reslizumab, benralizumab)
 - IL-4 and IL-13 antagonists (dupilumab)
 - Anti-IgE antibodies (omalizumab)
 - Rule
 - Any new initiation after Day 1
- Other protocol-prohibited immunomodulatory agents
 - Examples of medications: please refer to the protocol section 6.7.3. Prohibited Concomitant Therapy
 - Rule
 - Any new initiation after Day 1

Statistical Analysis Plan - SAP-APD334-206 - 13-Jan-2023

Electronic Signature Manifestation

This page is a manifestation of the electronic signature(s) used in compliance with the organization's electronic signature policies and procedures.

Signer Full Name	Meaning of Signature	Date and Time
PPD	Document Approval (I certify that I have the education, training and experience to perform this task)	13 Jan 2023 15:28:28 UTC
PPD	Document Approval (I certify that I have the education, training and experience to perform this task)	13 Jan 2023 16:17:59 UTC
PPD	Document Approval (I certify that I have the education, training and experience to perform this task)	13 Jan 2023 18:19:56 UTC

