3. STUDY DESIGN

3.1. Overall Design

This Phase 2 randomized, double-blind, multi-center study will evaluate the efficacy, safety, and PK of etrasimod compared with placebo for 24 weeks in adults with active EoE.

The study will consist of a Screening Period of up to 35 days, 24 weeks of double-blind treatment (Double-Blind Treatment Period), 28 weeks of active extended treatment (Extension Treatment Period), and 4 weeks of follow-up (Safety Follow-Up Period) for a total study duration of up to 61 weeks.

Eligible subjects will be randomized in a double-blinded fashion (3:3:2 ratio) to etrasimod 1 mg, etrasimod 2 mg, or matching placebo once daily. Randomization will be stratified by baseline history of esophageal dilation (yes/no) and concurrent PPI therapy (yes/no).

[figure not shown]
All subjects who complete the Double-Blind Treatment Period and meet eligibility criteria for the Extension Treatment Period may enter the Extension Treatment Period.

Subjects who were in etrasimod 1 mg or etrasimod 2 mg groups in the Double-Blind Treatment Period will continue the same etrasimod dose in the Extension Treatment Period. Subjects who were in the placebo group during the Double-Blind Treatment Period will be re-randomized (1:1 ratio) to etrasimod 1 mg or etrasimod 2 mg at entry into the Extension Treatment Period.

Subjects will have follow-up visits at 2 and 4 weeks after the last dose of study treatment after Week 52 or the Early Termination (ET) Visit.

A study design schematic is shown in [Figure 1](#).

Figure 1: Study Design

*Esophagogastroduodenoscopy
 EoE, eosinophilic esophagitis; ETR, etrasimod; F/U, follow-up; PBO, placebo.
 Numbers preceded by colons represent the randomization ratio.

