4.3. Eligibility Criteria for the Extension Treatment Period

Inclusion Criteria:

1. Completion of the Week 24 study visit (including EGD) including subjects who discontinued study treatment due to lack of clinical efficacy and started rescue therapy between Weeks 16 and 24. Rescue therapy must be discontinued on the day etrasimod is initiated in the Extension Treatment Period.
2. Compliance with study procedures during the Double-Blind Treatment Period as assessed by the Investigator
3. No notable safety concerns during the Double-Blind Treatment Period, as determined by the Investigator
4. Willing to comply with all study visits and procedures for the Extension Treatment Period

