6.7.4. Rescue Therapy

Any new medication or procedure used to treat new or worsened EoE symptoms is considered a rescue therapy. Rescue therapy should not be withheld if, in the opinion of the Investigator, failure to use/implement them would compromise the safety of the subject.

Subjects who discontinue between Week 16 and Week 24 due to lack of clinically meaningful efficacy will be provided the option to remain in the study. For these subjects, rescue therapy may be given until the end of the Double-Blind Treatment Period but must be discontinued upon entry in the Extension Treatment Period during which all subjects receive active treatment.

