8.2. Reasons for Discontinuation from the Study

The reason(s) for study discontinuation must be determined by the Investigator and recorded in the source documents and on the eCRF. If a subject discontinues for more than 1 reason, each reason should be documented in the source document and the most clinically relevant reason should be entered on the eCRF.

- AE
- Withdrawal by subject
- Study termination by Sponsor
- Pregnancy
- Non-compliance
- Lost to follow-up

- Lack of efficacy
- Death
- Other

All patients should be encouraged to complete the study. However, a subject may elect to discontinue study participation at any time for any reason without prejudice to their future medical care by the physician or the institution. If a subject withdraws consent, no further evaluation should be performed, and no additional data should be collected. The Sponsor may retain and continue to use any data collected before such withdrawal of consent. The Investigator should make a reasonable attempt to document the specific reason why consent was withdrawn and date of last study drug intake.

Subjects who discontinue treatment prematurely, regardless of the reason, should be instructed to return for an Early Termination and Follow-Up Visits. Refer to Section 9.6 and Section 9.5 for description of ET and follow-up procedures, respectively.

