9.5. Follow-Up/End of Study

All subjects will have follow-up visits for safety assessment at 2 and 4 weeks after the last dose of study treatment. All AEs should be recorded for 30 days after last dose of study medication (Section 10.6.8.1.9). Refer to Section 10.6.7.2 for details on the post-treatment follow up assessments and procedures for subjects who experience an ongoing AE of decreased lymphocyte count or infection.

In the event that a subject fails to attend any follow-up visits, all reasonable efforts will be made to contact the subject to ensure that he/she is in satisfactory health. All contacts and contact attempts must be documented in the subject's medical record.

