9.6. Early Termination

Subjects who discontinue the study prior to the end of the 24-week Double-Blind Treatment Period or the 28-week Extension Treatment Period (Week 52) will return to the study site for an ET Visit. The ET Visit should occur within 7 days of last dose and before initiation of any new treatments.

Site staff will work with subjects who withdraw early to obtain as much follow-up data as possible, including an EGD, if not done within 4 weeks, and PFTs and ophthalmic and OCT testing. If a subject discontinues due to pregnancy, they may not be required to complete the EGD and biopsy.

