15. STUDY MEDICATION EXPOSURE

Exposure to study treatment in weeks will be summarized for the Safety Set for the End of Double-Blind Period, Extension Period, and overall, respectively. For overall exposure to study treatment in the Double-Blind Treatment Period, the date of first and last study treatment administration will be taken from the Dosing Administration for Double-Blind Period eCRF. For the overall exposure to study treatment in the Extension Period, the date of first and last study treatment will be taken from the Dosing Administration for Extension Period eCRF. Exposure for the entire study may also be summarized, in which case, the earliest study treatment date from both periods will be used for the first date and the latest study treatment date in both periods will be used for the last date. Interruptions, compliance, and dose changes are not taken into account for duration of exposure. Total subject-years on study will also be summarized.

Dose interruptions will be recorded on the Dosing Administration for Double-Blind Period and Dosing Administration for Extension Period eCRFs. Overdoses will be recorded on the Overdose eCRF. The frequency and percentage of subjects who had at least one dose interruption, who had at least one dose interruption of >7 days, who

had at least one dose interruption of >14 days, who had one overdose, and who had >1 overdose will be summarized for the Safety Set.

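### SAP Appendix 4 does not say which follow-up period or last dose ends the counting of rescue, so off-drug rescue in Weeks 16 to 24 could go uncounted in the Week 24 analyses

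*SAP*

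**What the plan says.** **What counts as rescue.** SAP Appendix 4 sets out how the blinded reviewers identify rescue. It lists qualifying procedures and medications, mostly as new use after Day 1, and then makes an exception: "Use of rescue therapy during the follow-up period (beginning on or after the date of last study treatment administration) will not be considered" as rescue. SAP 17.1.2 refers the identification of rescue to this appendix.

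**Who may take rescue off drug.** Under Protocol 6.7.4, subjects who stop between Weeks 16 and 24 for lack of efficacy may stay in the study, and "rescue therapy may be given until the end of the Double-Blind Treatment Period". Protocol 4.3 admits to the extension those who completed the Week 24 visit with its endoscopy (EGD), "including subjects who discontinued study treatment due to lack of clinical efficacy and started rescue therapy between Weeks 16 and 24".

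**What happens to data after rescue.** The protocol synopsis sets continuous efficacy measures to missing after any rescue. Protocol 11.4.1 does the same for peak eosinophil count (PEC) at Weeks 16 and 24, and makes any rescue in the double-blind period a non-response. SAP 17.1.2 censors all efficacy endpoints from the start of rescue. None of these rules is limited to rescue taken on drug. SAP 3.3 declares no changes from the protocol.

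**Follow-up and last dose.** Protocol 3.1 gives subjects "follow-up visits at 2 and 4 weeks after the last dose of study treatment after Week 52 or the Early Termination" (ET) visit. Protocol 9.5 says: "All subjects will have follow-up visits for safety assessment at 2 and 4 weeks after the last dose of study treatment". For exposure in the double-blind period, SAP 15 says "the date of first and last study treatment administration will be taken from the Dosing Administration for Double-Blind Period eCRF"; for the entire study it uses the latest date across both periods.

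**Per Protocol Set.** SAP 5.5 excludes subjects whose rescue may affect the Week 16 primary endpoint, and Appendix 4 names Per Protocol exclusion as one of its two purposes. SAP 17.1.2 says rescue users can stay in the set if they break no other criterion.

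**The concern.** The parenthesis in Appendix 4 starts the exclusion at the last dose. It gives no end, does not name the Safety Follow-Up Period, and does not say which last dose is meant. The protocol deliberately keeps in the study a group who have had their last double-blind dose, are taking rescue, and still have a Week 24 EGD and diary scores. Two blinded reviewers could draw up different rescue lists for that group from the same sentence. If their rescue is not counted, results obtained on rescue are credited to the randomized arm at Week 24.

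The Per Protocol conflict is separate and does not depend on this sentence. One section treats rescue that may affect Week 16 as a reason for exclusion; the other says rescue alone is not one.

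**Working it through.** There is no figure in the plan to reproduce. The visible text gives no rescue counts, and the sample-size section is redacted. The check is of the text, followed by a sense of scale.

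**1. One subject under each meaning.** The subject's days are assumed: last double-blind dose Day 120, rescue starts Day 125, EGD Day 169. The EGD falls in the Week 24 window of SAP 6.4 (Days 156 to 183). The Week 24 Dysphagia Symptom Questionnaire (DSQ) score, calculated on Day 169, uses the preceding 14 diary days: 169 − 14 = 155 to 169 − 1 = 168.

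| Meaning of the sentence | Never re-dosed | Re-dosed in the extension (last dose Day 364, say) |
|---|---|---|
| Literal, last double-blind dose | 125 ≥ 120: not counted | 125 ≥ 120: not counted |
| Literal, last dose of the whole study | 125 ≥ 120: not counted | 125 < 364: counted |
| Safety Follow-Up Period after Week 52 or ET | counted | counted |

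For a subject never re-dosed the two last-dose dates coincide, so choosing between them does not help. Rescue started before the last dose is counted in every row.

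**2. Does another rule remove the values?** No. The first trigger in SAP 17.1.2 is stopping the study; this subject stopped only the drug. The other two triggers are rescue medication and rescue procedure, and what qualifies is left to Appendix 4. Where Appendix 4 does not count the rescue, Week 24 PEC and DSQ stay as observed.

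**3. Which rules does that break?** For PEC and DSQ, the synopsis. For PEC and Week 24 response, Protocol 11.4.1. In SAP 2.4 only the responder rows (key secondary estimands 3 and 4) address rescue after Week 16; they set later assessments to missing.

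**4. Which analyses are reached?** SAP 17.2.1 repeats the PEC ANCOVA at Week 24 and the DSQ mixed model through Week 24, as additional analyses. SAP 8.4 applies no type I error control. The visible SAP text lists no Week 24 responder analysis, although Protocol 11.4.1 provides for one. An observed Week 16 PEC taken before rescue is unchanged. Week 16 could be touched only through the imputation model, if Week 24 PEC enters it, or through the DSQ mixed model.

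**5. Scale, on assumed counts.** 96 × 3/8 = 36 per etrasimod arm and 96 × 2/8 = 24 on placebo. Assume complete Week 24 data, arms otherwise exchangeable, and *k* uncounted subjects who move from a typical rank to the best ranks of all 96, which is an extreme case. The other subjects then have mean rank 49 (*k* = 1) or 50 (*k* = 3). The SD of ranks 1 to 96 is √(96 × 97/12) = 27.86, so the unadjusted SE of 2 mg minus placebo is 27.86 × √(1/36 + 1/24) = 7.34. Lower rank means larger PEC reduction, so a positive shift is against etrasimod.

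- One on placebo: 49 − (23 × 49 + 1)/24 = +2.0 ranks (2.0/7.34 = 0.27 SE)
- Three on placebo: 50 − (21 × 50 + 6)/24 = +6.0 ranks (0.82 SE)
- One on 2 mg: (35 × 49 + 1)/36 − 49 = −1.3 ranks (0.18 SE)
- Three on 2 mg: (33 × 50 + 6)/36 − 50 = −4.0 ranks (4.0/7.34 = 0.54 SE)
- One in each of the three arms: (35 × 50 + 2)/36 − (23 × 50 + 2)/24 = 48.67 − 48.0 = +0.7 ranks (0.09 SE)

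A Week 24 response rate would move by 1/24 = 4.2 points per placebo subject or 1/36 = 2.8 per etrasimod subject. If rescue improves DSQ by an assumed 10 to 20 points, one subject moves the placebo mean by 10/24 = 0.42 to 20/24 = 0.83 points, or an etrasimod mean by 10/36 = 0.28 to 20/36 = 0.56.

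**The case against.** The strongest reply is that the sentence simply means the Safety Follow-Up Period, the only follow-up period either document defines. Its visits have no EGD and no diary monitoring in the protocol schedules, so ignoring rescue there is harmless. Protocol 6.7.4 places the disputed rescue inside the Double-Blind Treatment Period, and SAP 3.3 makes a departure from Protocol 11.4.1 unlikely to be intended. All of this stands, and it is the best account of intent. It does not cure the wording, which anchors on the last dose and is what the reviewers will apply.

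A reader might infer more than the documents support:

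- *That the Safety Follow-Up Period itself starts at the last double-blind dose, so rescue in the next 28 days is dropped.* Protocol 8.2 lends some support: "Subjects who discontinue treatment prematurely, regardless of the reason, should be instructed to return for an Early Termination and Follow-Up Visits". But that section concerns leaving the study, Protocol 9.6 ties the ET visit to "Subjects who discontinue the study prior to the end of the 24-week Double-Blind Treatment Period", and 6.7.4 keeps this group in. The tension is a reason to clarify; it does not establish the reading.
- *That the SAP contradicts itself because Appendix 4 also counts new use after Day 1 and 17.1.2 censors after rescue.* Within the SAP this is a rule with an exception, since 17.1.2 relies on Appendix 4. On the literal reading the direct conflict is with the protocol.
- *That the dose will be selected on contaminated Week 24 values.* Protocol 6.5 uses the dose selection analysis to time unblinding. It does not say that Week 24 values decide the dose, and the primary and secondary endpoints are all at Week 16.

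On the Per Protocol Set, the two sections can be partly reconciled: SAP 5.5 covers only rescue that may affect Week 16, and 17.1.2 is permissive. The conflict remains for exactly that kind of rescue.

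**Conclusion.** The concern holds as an ambiguity that should be closed. On the likely reading, rescue in Weeks 16 to 24 is counted and nothing conflicts. On the literal reading it is not counted, either for those never re-dosed or for everyone who stopped drug before starting rescue, and their Week 24 PEC and DSQ are analysed against the protocol's own rule. The consequence is confined to the additional, unadjusted Week 24 analyses, with at most an indirect effect at Week 16.

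Its size and direction are unknown. The documents give no rescue counts, and the direction depends on which arm has more off-drug rescue. With 0 to 3 such subjects in one arm, under the extreme assumption above, the PEC rank comparison of 2 mg with placebo moves by at most 0.82 SE against etrasimod or 0.54 SE in its favour; balanced use moves it very little. The conflict between SAP 5.5 and 17.1.2 is real on any reading of Appendix 4.

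**What to change.** Both changes are to analysis wording and leave untouched when rescue may be given.

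1. In Appendix 4, state that qualifying therapy started after Day 1 and before an efficacy assessment is an intercurrent event for that assessment and later ones, on or off study drug. Apply this to both the double-blind and the extension periods, because the appendix also governs the Week 32 and Week 52 efficacy assessments. Limit the exclusion to therapy started after the subject's last efficacy assessment, that is, in the Safety Follow-Up Period.
2. Reconcile SAP 17.1.2 with SAP 5.5, so that one rule says whether rescue that may affect the Week 16 endpoint removes a subject from the Per Protocol Set.

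The cost is a few sentences in the SAP. No new data are needed, but the change must precede finalisation of the rescue list, which Appendix 4 places before unblinding. If the Safety Follow-Up reading was always intended, the first change only writes it down.
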